12. STATISTICAL CONSIDERATIONS

12.1. Study Design/Endpoints

We propose to test the utility of fast MRI scans to identify cardiotoxicity in patients treated with Chemotherapy for BrC or Lymphoma (taking advantage of existing clinical trial resources). This study allows us to address our over-arching goal: to determine the optimal implementation (alone or in combination with other tests) of our fast MRI processes for forecasting CV injury in patients treated with Chemotherapy in community hospitals through performance of a Phase II comparative effectiveness study within an ongoing clinical trial.

Primary endpoints include LVESV, LV end diastolic volume (LVEDV), LV mid-wall circumferential strain, T1 & T2 Mapping, PWV, aortic wall thickness compared between fast MRI & ECHO and Troponins.

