12.3. Analysis Plan

Aim 1: We will estimate the correlations between the baseline to 2-month changes in 3 measures from the 10-min MRI (LV volumes, T1/T2 times and aortic PWV) and the baseline to 6-month changes in LVEF as measured by a 45-min MRI. With 30 patients available, we will have 80% power to detect a correlation of 0.5 between each of the baseline to 2-month changes in 10-min MRI measures with the baseline to 6-month change in LVEF. To examine whether the variability of the two MRI assessments (10-min and 45-min) is comparable we will calculate variance ratios for different CV measures and determine their comparability (i.e., they will be considered comparable if they fall between 0.8 and 1.2).

Aim 2: The second Aim will focus on determining the association between early changes in our 10-min MRI as well as changes in conventional measures of CV dysfunction including: 45-min MRI, ECHO (including PWV) and cardiac serum biomarker (TnI) at 2-months and 6-month deteriorations in LVEF. In 2 fashions, we will estimate the change in each of the novel and conventional measures after 2-months and determine how well they predict the baseline to 6-month change in LVEF. First, we will estimate the correlation between the baseline to 2-month changes for each measure with the baseline to 6-month change in LVEF. Also, we may fit linear regression models to estimate the relationship of these early changes in measures with the 6-month change in LVEF adjusting for patient level characteristics. Next, we will dichotomize the patients into those who exhibit a drop in LVEF from baseline to 6 months (absolute level of EF below 50% or a 10% or greater drop in LVEF) and those who don't. We will then perform a series of 2 sample t-tests to see whether the mean change after 2 months in LVEF and the other measures is different for patients who exhibit a drop in LVEF at 6 months.

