Aim 3: We will fit a series of exploratory multiple logistic regression models where the outcome measure will be the binary variable LVEF drop baseline to 6-months (yes/no) and each model will begin with a key predictor (10-min MRI measures, 45-min MRI measure or ECHO measure) and then we will add in additional clinical and patient level characteristics into the models to determine whether there is a combination of clinical and demographic characteristics that enhance the prediction of LVEF drop for each measure of CV dysfunction. ***We recognize that with a limited sample size these models will provide initial information about variables that may be useful in predicting the outcome of interest.*** In addition, we will consider using alternative model building strategies such as artificial neural network (ANN) in order to determine whether there are combinations of the measures taken at baseline and 2-months that predict a drop in LVEF at 6 months. For these analyses we will have over 80% power to detect correlations of 0.50 between the baseline to 2-month changes in each measure and the baseline to 6-month changes in the outcomes assuming a 2-sided test with $\alpha=0.05$ and 30 patients. In addition, we will have 80% power to detect a difference between groups (those with a 6-month drop in LVEF vs those without a 6-month drop) equal to 1.06 standard deviations for the measure of interest assuming a 2-sided test with $\alpha=0.05$ if roughly half of the patients exhibit a drop in LVEF after 6 months. If only 33% ($n=10$) exhibit a drop at 6-months then we will have 80% power to detect a difference of 1.12 standard deviations. The primary goal of this Aim for this study is to determine which measures exhibit a correlation with the 6-month outcome and show some predictive strength in the logistic regression models. Those measures that meet these criteria will then be considered in Phase II, which will allow us to directly compare the predictive strength of each measure with each other. In Phase II, when our sample size will increase to 150 patients, we will be able to fit more robust statistical models to develop predictive equations for identifying patients at risk for a drop in LVEF based on their initial and 2-month measures. With the larger sample size we will have over 80% power to detect correlations between the predictors and 6-month change in LVEF of 0.23 or larger. In addition, we will be able to mean differences in patients with or without a 6-month drop in LVEF of less than 0.58 standard deviations if at least 20% ($n=30$ out of 150) of the patients exhibit a 6-month drop in LVEF.

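### The baseline-to-6-month LVEF outcome contains the baseline-to-2-month predictor window, so LVEF and volume changes at 2 months are partly the outcome seen early and are credited as forecasting

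*Combined protocol and SAP*

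**What the plan says.** Section 12.1 gives the goal as finding the best use of the fast MRI "for forecasting CV injury in patients treated with Chemotherapy in community hospitals". Section 12.3 then sets these analyses:

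- **Aim 1** correlates 2-month changes in LV volumes, T1/T2 and PWV with the change in LVEF from baseline to 6 months.
- **Aim 2, correlations:** "estimate the correlation between the baseline to 2-month changes for each measure with the baseline to 6-month change in LVEF".
- **Aim 2, groups:** the plan will "dichotomize the patients into those who exhibit a drop in LVEF from baseline to 6 months", defined as "absolute level of EF below 50% or a 10% or greater drop in LVEF) and those who don't". T-tests are then planned with this purpose: "see whether the mean change after 2 months in LVEF and the other measures is different for patients who exhibit a drop in LVEF".
- **Aim 3:** "the outcome measure will be the binary variable LVEF drop baseline to 6-months (yes/no"). On the predictor side, "each model will begin with a key predictor (10-min MRI measures, 45-min MRI measure or ECHO measure").

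The optional Aim 2 regression adjusts for patient-level characteristics, and the Aim 3 models add clinical and patient-level characteristics. Section 12.3 does not separate drops already present at 2 months from later ones, does not use the 2-to-6-month change as an outcome, and does not adjust for LVEF at 2 months. Measures that correlate with the 6-month outcome and show some predictive strength are to be considered for Phase II.

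**The concern.** The change from 0 to 6 months is the sum of the change from 0 to 2 and the change from 2 to 6. When the predictor is the 0-to-2 change in LVEF, one of these terms stands on both sides. LV volumes share this, because LVEF is computed from them. A measure can then look predictive because a fall had already happened and lasted, with no information on what follows.

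The documents give reason to expect early falls. Section 3.1 places the 2-month visit after chemotherapy has been received. Section 2.1.4 reports that LVEF change at 1 month tracks the change at 6 months, and that 25 of 44 patients (57%) had a drop at 6 months.

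Aim 2 is a comparison of measures, and the results inform which go forward. Section 2.1.2 values T1 because its changes come before LVEF decline. A marker of that kind, which speaks to decline after 2 months, is at a disadvantage against LVEF in these analyses.

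**Working it through.** **1. The plan's own figures reproduce** (two-sided α = 0.05).
- Correlation 0.50, n = 30, Fisher z: Φ(atanh(0.5)·√27 − 1.96) = 81.4%.
- Noncentral t: 1.06 SD at 15 v 15 gives 80.0%; 1.12 SD at 10 v 20 gives 79.7%.

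The power statements are not in error. They do not distinguish forecasting from detection.

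**2. Assumptions.** Baseline LVEF has mean 62 and SD 5. Change in months 0–2 (mean m₁, SD s₁) and in months 2–6 (m₂, s₂) are independent, so early change says nothing about later change. There is no scan error, and the 10% drop is read as EF points. The drop rule is that of Section 12.3.

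**3. Correlations in closed form.**
- 2-month LVEF change with 6-month change: r = s₁/√(s₁² + s₂²). For s₁ = 4, s₂ = 5.6: 4/√(16 + 31.36) = 0.58.
- 2-month LVEF change with the 2-to-6-month change: 0 by construction.
- A non-LVEF marker correlating 0.5 with the later change, with the planned 6-month change: r = 0.5·s₂/√(s₁² + s₂²). Same scenario: 0.5 × 5.6/6.88 = 0.41.

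**4. Drop groups by simulation** (2,000,000 patients per scenario).

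| m₁/s₁, m₂/s₂ | 6-month drop | Of these, present at 2 months | LVEF change: r | LVEF: SD, all | LVEF: SD, without patients in drop at 2 months | Marker: r | Marker: SD, all |
|---|---|---|---|---|---|---|---|
| −2/4, −4/5.6 | 34% | 18% | 0.58 | 0.99 | 0.86 | 0.41 | 0.66 |
| −3/5, −3/5 | 35% | 35% | 0.71 | 1.29 | 1.00 | 0.35 | 0.57 |
| −4/5, −2/4 | 33% | 48% | 0.78 | 1.46 | 1.07 | 0.31 | 0.49 |
| −4/6, −4/6 | 46% | 42% | 0.71 | 1.30 | 0.96 | 0.35 | 0.57 |

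On the plan's 10 to 15 drops, 18% to 48% is about 2 to 7 patients (0.18 × 10 = 1.8; 0.48 × 15 = 7.2). By the Fisher z formula at n = 30, r = 0.58 has 93% power, while r = 0.31 to 0.41 has 39% to 61%.

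**5. Excluding early drops is not enough.** Between 73% (1.07/1.46) and 87% (0.86/0.99) of the LVEF difference remains, although true forecasting is zero. The outcome is still measured from baseline: a patient 8 points down at 2 months needs only 2 more to count as a drop.

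**6. Adjustment does separate the two.** In the same simulations, with 6-month LVEF adjusted for baseline and 2-month LVEF, the marker of later decline has a partial correlation of 0.50. A marker correlating 0.5 with early change only has 0.00. In the planned analysis that early-change marker scores 0.29 to 0.39 (0.46 to 0.63 SD).

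**7. Sensitivity.** With scan error of SD 2 to 3 points and mean total falls of 4 to 8 points, LVEF correlates 0.44 to 0.77 with the planned outcome and −0.17 to −0.24 with the later change; 18% to 64% of drops are present at 2 months. Reading 10% as relative, without scan error, gives 29% to 60% present.

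**The case against.** Baseline-to-6-month deterioration is the target that Aims 1 and 2 state, and early detection of injury is also a stated purpose (Sections 1, 2 and 12.1). A 2-month scan that shows a lasting drop serves that purpose. Aim 3 is labelled exploratory, the plan acknowledges its limited sample size, and direct comparison of predictive strength is left to Phase II. This stands: it is a reason to keep the planned analyses and it lowers the severity. It does not settle what the results may be called, because the overall goal is also worded as forecasting.

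A reader might infer four stronger things that the documents do not support.

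- **That T1/T2, PWV and troponin gain nothing from early drops.** Any marker that tracks early injury gains something (step 6), and Section 2.1.2 describes T1 change as marking such injury. The gain is smaller than that of LVEF.
- **That LVEF would reach the plan's detectable difference only because of patients already in drop.** The third scenario leaves 1.07 SD without them, inside the plan's 1.06 to 1.12 range, and all inputs are assumed.
- **That the plan ranks measures, so that credit to LVEF displaces others.** Section 12.3 says only that qualifying measures will be considered.
- **That removing patients already in drop would leave a true forecasting result.** Step 5 shows otherwise.

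**Conclusion.** The point holds. The predictor window lies inside the outcome window throughout Section 12.3: in the Aim 1 and Aim 2 correlations, the Aim 2 t-tests and the Aim 3 models. Nothing in the plan separates a drop seen at 2 months from one that develops later. That follows from the text alone.

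The size does not. It rests on assumed means and SDs, independent early and later change, and no scan error. On those inputs, LVEF change with no forecasting value shows r of 0.58 to 0.78 and 1.0 to 1.5 SD. A marker that does carry information on later decline shows r of 0.31 to 0.41 and 0.49 to 0.66 SD. The true share of drops already present at 2 months is unknown until the pilot reports it.

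This should be changed before analysis. It does not invalidate the pilot or its power figures; it limits what a positive result can be said to show.

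**What to change.** Keep the planned baseline-to-6-month analyses and describe them as association or early detection. Add to Section 12.3, using the LVEF from the fast MRI already scheduled at 2 months:

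1. **Counts.** Report how many 6-month drops were already present at 2 months and how many were new.
2. **Adjusted results.** Beside each planned correlation or model, report the association of each 2-month measure with 6-month LVEF, adjusted for baseline and 2-month LVEF. This asks whether the measure adds to the LVEF already seen. Fast-MRI LVEF change cannot be tested this way, since it is fixed by the two adjusting values. Show the 2-to-6-month LVEF change descriptively, and note that shared 2-month scan error pushes the LVEF measure's own correlation with it towards negative values.
3. **Wording.** Describe a measure as forecasting later decline only on the basis of item 2, and show both sets of results when choosing measures for Phase II.

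Excluding patients already in drop at 2 months may be shown as a sensitivity analysis, with a statement that it does not remove the overlap.

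The cost is SAP wording and extra analysis, with no new visit, scan or patient. The added results are less precise and so descriptive at N=30: if 3 of 10 drops were already present, the exclusion subset is 7 v 20 and detects 1.28 SD at 80% power, against 1.12 SD for 10 v 20. Scan error in the 2-month LVEF also makes the adjustment incomplete, which the report should say.

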12.5. Power and Sample Size considerations for the primary hypothesis

This is pilot trial of 30 subjects. Because of the budget limits of a pilot trial, we did not choose the sample size specifically to detect a 0.5 correlation – but felt that this was a reasonable sample size and with that sample size we could detect a correlation of 0.5. We aim to determine which measures exhibit a correlation and which also show some predictive strength in the logistic regression models. We will use this for the design of our Phase II study which will show the predictive strength of each measure and will be sufficiently powered.

12.6. Evaluation of Toxicity

All participants will be evaluable for toxicity from the time of their first MRI.

